After providing informed consent, participants will complete an assessment including clinical interviews for TBI, chronic pain, and cognitive function; self-report instruments measuring chronic pain, TBI outcomes, suicidality, violence/aggression, drug and alcohol use, mental health, demographics, military experience, behavioral activation (BADS-SF) and medications/treatment, and an EEG/ECG reading. Participants will be assigned to one of three groups (n=100 in each): neurofeedback [using a (Muse) portable EEG headset and Mobile Muse: the brain sensing headband Neurofeedback app created by our group], mindfulness (using a mindfulness app created by our group, derived from the DoD and VA Mindfulness Coach app), or unstructured relaxation/control (using a relaxation app, also created in-house). All participants will receive an iPod Touch, be trained to use their respective app and instructed to practice 10 minutes a day, 4 times a week for 12 weeks, and be set up to receive reminders to practice from their iPod Touch or smartphone calendars. If participants prefer to receive reminders on their smartphone, they will be instructed to add a reminder in the calendar app on their smartphone that reminds them to complete their 10-minute practice sessions 4 times per week. Participants will be asked to report their current level of pain, stress, and anger before and after each session. Study coordinators will conduct two home visits (week 1 and week 6) and two phone calls (week 3 and week 9) to reinforce training, troubleshoot difficulties, observe participants utilizing the intervention in their home environment, and collect data on usability and tolerability. Follow-up data will be collected upon completion of the intervention at 12 weeks and again at 24 weeks. During both follow-up visits, veterans will complete clinical interview, pain assessment, self-report instruments including current traditional and alternative pain treatments, and EEG/ECG reading. Due to COVID-19, some participants will be asked to complete visits remotely. Coordinators will conduct "home visit" phone calls and will conduct baseline (screening/enrollment) follow-up interviews over the phone or via WebEx/Zoom, as needed. During these visits, there will be no EEG or HRV readings or cognitive testing. Data will be downloaded from the iPods once they are shipped back to our Duke offices following the participants' completion of the intervention at 3 months. For remote follow-up visits, participants will complete part of the visit over the phone and/or WebEx/Zoom, emailed a Qualtrics link to complete survey questionnaires, and emailed a FedEx label for shipping study equipment. Intervention Training will be combined with Home Visit 1 for remote visits, and we will follow up with a short phone call ~1 week later to assess for adverse events and safety measures. We will also ask two home visit questions, "Can you give any examples of specific times or situations in which the intervention was helpful?" and "What problems, if any, have you had using the app since you last talked with us?"

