Neurofeedback: The proposed study intervention for the neurofeedback group involves two components, the Muse portable EEG headset and the 'Mobile Neurofeedback' app. Study participants engage in neurofeedback to practice meditation and induce relaxation, with the goal of reducing pain symptoms. Participants will be given a mobile neurofeedback headset, the Muse, which connects to the 'Mobile Neurofeedback' app via Bluetooth. During a 'Mobile Neurofeedback' session, individuals receive continuous neurofeedback, rewarding them whenever EEG signals move into patterns of brain activity that indicate a calm, relaxed state. Using 'Mobile Neurofeedback,' participants can select a soothing sound to help them gauge how relaxed they are and track neurofeedback progress. Participants will be instructed to use Muse + 'Mobile Neurofeedback' a total of 10 minutes a day, 4 times a week for 12 weeks.

Mindfulness Training: The study intervention for the mindfulness group uses a Mindfulness app created by our study team, derived from the "Mindfulness Coach" app, which was created by the Department of Defense's National Center for Telehealth and Technology in partnership with the Department of Veterans Affairs National Center for PTSD. The app was modified to function and appear aesthetically similar to the Mobile Neurofeedback app. This app enables individuals to practice the foundational features of mindfulness, which as described above, has been shown in other contexts to be effective for reducing stress, improving emotional balance, increasing self-awareness, helping with anxiety and depression, and coping more effectively with chronic pain. Using an iPod Touch received at their initial study visit, individuals will perform the app's Mindful Breathing and Body Scan exercises. The Mindful Breathing exercise guides users to focus their attention on their breath, to non-judgmentally notice when they become distracted, and to then direct their attention back to their breath. The Body Scan exercise guides participants to direct their attention to different parts of their body, noticing the sensations they feel without judging or trying to change them. These have both been adapted into 10-minute audio-guided exercises with step-by-step instructions. Participants will also have the opportunity to select a relaxing musical or

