ambient background sound, identical to the choices in the Mobile Neurofeedback app, which will play in the background of the guided exercises. Participants will be instructed to complete these sessions 4 times a week for 12 weeks.

Unstructured Relaxation (control group): The control group will use a Relaxation app, which is designed to promote relaxation. The Relaxation app, also created by our study team, is aesthetically similar to the Mobile Neurofeedback app and offers the same relaxing background sounds with nature images. To create the most relaxing experience, users can choose a background sound and adjust the volume. Sessions are set for 10 minutes, and participants will be instructed to complete these sessions 4 times a week for 12 weeks.

All participants will be asked to report pain, anger, and stress symptoms before and after each session. All apps include their own logging systems to track usage. Research staff will also directly collect this weekly app usage data from participants' iPods a total of six times (at the two home visits, the two phone calls, and at the 3 and 6-month follow-up visits) during the study period. Devices will be labeled according to FDA requirements for non-significant risk devices. To preserve blinding to study condition, the same label will be used on all devices and will include the most significant side effects possible from any of the interventions.

Risk/Benefit Assessment

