We believe that this study poses minimal risk to participants and that the risk-to-benefit ratio in the proposed study is acceptable. Anticipated risks related to neurofeedback include drowsiness after neurofeedback practice sessions and minor discomfort due to practicing neurofeedback. There is also the chance that participants may experience headaches, dizziness, fatigue, tingling sensations, negative feelings such as anxiety or frustration, or increased risk of seizures among individuals with epilepsy or seizure disorder, although these side effects are rare. To minimize these risks, participants with a history of seizures will be excluded, and all participants will be instructed to practice neurofeedback at a time when they will not need to perform tasks that require high levels of alertness, such as driving or operating machinery. Participants are warned about each side effect prior to enrolling in the study and reminded again during neurofeedback training. Veterans will be asked if they have experienced any side effects during each scheduled study interaction and are instructed to contact research staff if they experience any of these adverse effects in conjunction with using the neurofeedback. Participants are instructed to discontinue use of neurofeedback if any of these adverse effects begins to affect their daily activities.

Mindfulness training or the control relaxation condition do not present a potential for serious risk to the health, safety, or welfare of a subject. It is possible that the process of learning mindful awareness may temporarily increase feelings of discomfort due to increased awareness. Veterans in the mindfulness and relaxing sounds groups will be instructed to discontinue the intervention if they experience any previously unknown adverse effects, to seek medical assistance if they require it, and to report the adverse effects to the researchers.

It is possible that some participants may become upset by interview questions, i.e., in response to

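### A common device label cannot blind the headset arm to its intervention, and side-effect reminders and between-visit reporting instructions differ by arm

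*Combined protocol and SAP*

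**What the plan says.** **Blinding.** The only sentence on blinding is at the end of Study Interventions: "To preserve blinding to study condition, the same label will be used on all devices". The label "will include the most significant side effects possible from any of the interventions". Two further masking measures appear in the same section. For the mindfulness arm, "The app was modified to function and appear aesthetically similar to the Mobile Neurofeedback app". The control app "is aesthetically similar to the Mobile Neurofeedback app and offers the same relaxing background sounds with nature images". No section says who is blinded: participants, coordinators, outcome assessors or analysts.

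**Equipment and contact.** Under Neurofeedback: "Participants will be given a mobile neurofeedback headset, the Muse, which connects to the 'Mobile Neurofeedback' app via Bluetooth". The mindfulness and relaxation arms are described with an app on an iPod, and no sham headset is mentioned. Under Design & Procedures, coordinators make two home visits, where among other things they "observe participants utilizing the intervention in their home environment". Coordinators also conduct the remote follow-up interviews, and no separate blinded assessor is named.

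**Side effects.** The neurofeedback paragraph of Risk/Benefit Assessment says: "Participants are warned about each side effect prior to enrolling in the study and reminded again during neurofeedback training". It asks for contact with staff about any of the listed effects that occur with neurofeedback use. The next paragraph gives the other two arms an instruction tied to effects not known beforehand. Questioning about side effects at every scheduled contact (Risk/Benefit Assessment), about seizures at weeks 1, 3, 6, 9 and 12, and about all adverse reactions (both in Data & Safety Monitoring) is worded for participants generally.

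**The concern.** A label can keep itself from revealing the arm. It cannot conceal that one participant wears an EEG device that responds to brain signals while another listens to sounds. Hypothesis 1 concerns pain that veterans report at 3 months, so any difference in expectation between a brain-sensing headset and a sound app enters the neurofeedback-control contrast directly. Nothing in the plan measures that expectation. A report that repeats the blinding sentence could lead readers to credit the contrast with protection it does not have.

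The second issue is adverse-effect ascertainment. If one arm hears the list again at training and is asked to call about items on it, while the others are given a different trigger, volunteered reports of common complaints such as headache or drowsiness may differ between arms for reasons unrelated to the interventions.

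**Working it through.** **1. The sections side by side**

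| Feature | Neurofeedback | Mindfulness | Relaxation (control) |
|---|---|---|---|
| Headset with live EEG feedback | Yes | Not described | Not described |
| Session task | Feedback on brain activity | Guided audio exercise | Background sounds |
| App appearance and sounds | Reference app | Matched | Matched |
| Common label | Yes | Yes | Yes |
| Warning before enrolment | Yes | Yes (precedes assignment) | Yes (precedes assignment) |
| Side-effect reminder at training | Yes | Not described | Not described |
| Scheduled questioning | Yes | Not restricted by arm | Not restricted by arm |
| Between-visit reporting trigger | Listed effects | Effects not known beforehand | Effects not known beforehand |

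The first two rows show that matching the label and app appearance does not mask the intervention in the neurofeedback arm. Mindfulness and control differ in task but not in equipment. The reminder and between-visit reporting rows differ by arm in the text; the warning and scheduled-questioning rows do not.

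**2. The plan's own figure**

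Inputs from Data Analysis & Statistical Considerations: 100 per arm, 10% attrition, d = 0.42, 80% power. The significance level is not stated; two-sided 0.05 is assumed here.

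- Analysed per arm: 100 × 0.90 = 90.
- Standard error of a difference in SD units: √(2/90) = 0.149.
- Power: Φ(0.42/0.149 − 1.960) = Φ(0.857) = 80.4%. The t-test version gives 80.0%.

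The stated 80% is reproduced, and this point does not affect it.

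**3. Illustration of what a reporting shift would do**

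The documents give no size for expectation bias, so the shifts b below are assumptions. With no true effect, the chance of a significant result is Φ(b/0.149 − 1.960) + Φ(−b/0.149 − 1.960).

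| Assumed shift b (SD) | b/0.149 | False-positive rate |
|---|---|---|
| 0 | 0 | 5.0% |
| 0.05 | 0.335 | 6.3% |
| 0.1 | 0.671 | 10.3% |
| 0.2 | 1.342 | 26.9% |
| 0.3 | 2.012 | 52.1% |

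The noncentral t gives 10.2%, 26.6% and 51.7% for the last three rows. For scale, 0.2/0.42 = 0.48, so a 0.2 SD shift is about half the effect the trial is sized to detect. This is an unadjusted two-group calculation; the plan's mixed model adjusts for baseline, so the exact percentages would differ.

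**The case against.** The blinding sentence follows a sentence on device labelling. It can be read modestly: one label is used so that the label does not give the arm away. The apps are also matched in look, sounds, session length and schedule, and every participant receives an iPod. The control app is itself meant to promote relaxation, so a participant may know which app is in use without knowing that it is the comparator. All of this stands. It means the allocation's role in the trial may remain hidden even though the intervention does not. It does not rescue a general claim of blinding to study condition, because the headset is evident to the wearer and to coordinators.

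On side effects, a reader might infer that adverse effects are elicited unequally throughout, including at the home visits. The documents do not support that: scheduled questioning is not restricted by arm, and the label and the pre-enrolment warning reach everyone. A reader might also infer that the mindfulness and relaxation arms are to report nothing except effects not known beforehand. The text contains no such limit, and the scheduled questioning comes on top. Because few effects are listed for those two arms, the phrase may even be meant to cover headache or drowsiness; yet these arms have already been warned of the full list, which points the other way. That ambiguity is itself a reason to reconcile the sections. Finally, the missing reminder in those arms is inferred from silence; training scripts are not in the documents.

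The assumed shifts are not evidence of bias, and rewording the text would not remove any bias that exists. Both points are accepted.

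**Conclusion.** The point holds in limited form. Neurofeedback versus control on self-reported pain is not blinded as to the intervention used, and the plan does not say who, if anyone, is blinded. It would be going too far to say that the whole pain analysis is unblinded: the headset argument does not touch mindfulness versus control, and whether participants know which arm is the control is not stated.

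As documented, spontaneous adverse-effect reports are not comparable across arms, because the training reminder and the between-visit trigger differ. This does not extend to answers given at scheduled contacts, apart from any carry-over from the reminder.

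No size can be given from the documents. The false-positive rates of about 10%, 27% and 52% rest on assumed shifts of 0.1, 0.2 and 0.3 SD, an assumed two-sided 0.05 level and 90 analysed per arm. They show sensitivity, not a demonstrated error. A reader might also infer a problem with the handling of EEG recordings; no section describes one, and none is claimed here.

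**What to change.** 1. At training in all three arms, give the same side-effect reminder, using the list already on the common label, with the same request to report any of those effects. Reconcile the adverse-effect instructions in Study Interventions, Risk/Benefit Assessment and Data & Safety Monitoring. The instructions on stopping also differ between these sections and need reconciling by the sponsor; no stopping rule is proposed here.
2. Replace the blinding sentence with a statement of who is and is not blinded, to what, and what participants are told about the arms. State that the neurofeedback contrast tests the app-plus-headset package, while mindfulness versus control is matched on equipment.
3. Optionally, ask one expected-benefit question in all arms after training and before the first session. Report it descriptively by arm beside the 3-month contrast, not as an adjustment.

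The cost is a common script, revised text and, if adopted, one question. No sham device, extra staff or change in sample size is needed. The downsides are a less favourable description of blinding and a small nocebo risk in the two lower-risk arms, which already meet these effects on the label and in the pre-enrolment warning. If enrolment is complete, the corrected blinding statement can still be made, and the difference in instructions can be disclosed when adverse effects are reported.

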**Neuromodulatory Treatments for Pain Management in Veterans With Complex TBI
Using Mobile Technology**

NCT03418129

Document Date: December 5, 2022

Purpose of the Study

Aim 1: Examine the effectiveness of mobile interventions for reducing pain symptoms in Veterans with complex TBI. Hypothesis 1: Given preliminary data and empirical support for neurofeedback and mindfulness, we hypothesize that Veterans in the two intervention groups will report less pain at 3 months compared to Veterans in the control group.

Aim 2: Investigate the impact of neurofeedback and mindfulness on brainwave activity in Veterans with complex TBI and chronic pain. Hypothesis 2: Given research on electroencephalogram (EEG) and pain, we hypothesize that Veterans in the two intervention groups will show increased (8–12 Hz) alpha power at 3 months compared to Veterans in the control group.

Given connections to adverse outcomes, we will explore whether neuromodulatory interventions impact: (i) risk behaviors, with a hypothesis of lower levels of suicidality, aggressiveness/ violence toward others, and use of alcohol and drugs for the neurofeedback and mindfulness groups compared to the control group; and (ii) heart rate variability (HRV), with a hypothesis of significantly greater improvements in HRV compared Veterans to the control group.

Background & Significance

Traumatic brain injury (TBI) and chronic pain are common and serious health problems for Veterans of Operations Enduring Freedom, Iraqi Freedom, and New Dawn (OEF/OIF/OND) and often co-occur, leading to poor post-deployment adjustment. Pharmacological treatments for pain elevate risk of opioid abuse, and research suggests veterans perceive barriers to existing non-pharmacological, clinic-based treatments.

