questions that ask about sensitive personal information or traumatic experiences. Participants will be made aware of what to expect during study procedures prior to their participation, and they will be informed in the consent form that the procedures may potentially lead to more distress. Participants will also be informed that they may discontinue their participation at any time. Interviews will be conducted by research staff trained in interviewing and de-escalation. Veterans who become upset during the interview will be informed that they need not complete the interview and that our staff can make arrangements for them to see a clinician at the mental health center. Finally, there is a risk of breach of confidentiality associated with any research. See section 14 below regarding steps to minimize the risk of breach of confidentiality.

This study advances the field by testing the efficacy of portable, technology-based neuromodulatory approaches by permitting Veterans to manage pain in a self-directed manner outside a clinic setting. This project will be the first to test the efficacy of such interventions in a population of Veterans reporting frequent and intense chronic pain, namely, post-9/11 Veterans with complex TBI. If we find that neurofeedback or mindfulness delivered via mobile technology is effective in reducing pain, our research team is uniquely skilled to examine whether the intervention also reduces maladaptive behaviors such as drug abuse, violence, and suicide. Both self-directedness and mobility address barriers Veterans report with traditional treatments. Developing alternative treatments would also reduce dependence on pharmacological treatments, reduce the need for clinic visits, minimize associated stigma, and allow patients to feel actively engaged in their own treatment. Participants may also benefit personally from being in this research study by experiencing reduced pain symptoms.

Data Analysis & Statistical Considerations

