After accounting for a 3-month attrition rate of 10%, our targeted sample of 300 (100 in each treatment arm) will have 80% power to detect an effect size equivalent to Cohen's $d = 0.42$. This corresponds closely to findings from a published clinical trial of neurofeedback to reduce chronic pain (Jensen et al., 2013), which found 3-month improvements in pain intensity (0-10 rating scale) equivalent to Cohen's $d = 0.38$. Unless otherwise specified, we will fit a mixed longitudinal model with change from baseline to 3 months and 6 months as the response variable, pain stratification group as a blocking factor, randomized treatment as the between-subjects factor, month as a within-subjects factor, the interaction between treatment and month, and baseline score as a covariate. We hypothesize Veterans in the two intervention groups will report less pain at 3 months compared to Veterans in the control group. We also hypothesize Veterans in the two intervention groups will show increased (8–12 Hz) alpha power on EEG at 3 months compared to Veterans in the control group.

Data & Safety Monitoring

Participants will be screened and excluded from study participation if they have epilepsy/seizure disorder. Potential participants will be asked about seizures twice prior to enrollment in the study intervention: once on the phone screen and again during the initial study interview. Participants will be told to discontinue the study intervention if they develop a seizure disorder or have a seizure. Participants will also be asked about seizures at weeks 1, 3, 6, 9, and 12 of study participation, and will be told to stop the intervention if they report one.

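### Does the 80% power claim fall short because it covers one arm against control while Hypothesis 1 names two intervention arms?

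*Combined protocol and SAP*

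**What the plan says.** Aim 1 in Purpose of the Study, repeated under Data Analysis & Statistical Considerations, states the hypothesis as one sentence: "Veterans in the two intervention groups will report less pain at 3 months compared to Veterans in the control group". Design & Procedures sets equal allocation, 100 per arm, to neurofeedback, mindfulness and a relaxation control.

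The sample-size statement in Data Analysis & Statistical Considerations allows for 10% loss by 3 months and says that "our targeted sample of 300 (100 in each treatment arm) will have 80% power to detect an effect size equivalent to" d = 0.42. It calls this close to a published neurofeedback trial "which found 3-month improvements in pain intensity (0-10 rating scale) equivalent to" d = 0.38.

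The analysis is a longitudinal mixed model of change from baseline, with "randomized treatment as the between-subjects factor, month as a within-subjects factor, the interaction between treatment and month, and baseline score as a covariate", plus a pain-stratum blocking factor. The documents give no alpha or sidedness, name no contrast, and set no rule for a result in which only one intervention beats control.

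Risk/Benefit Assessment looks ahead to further work with the words "If we find that neurofeedback or mindfulness delivered via mobile technology is effective in reducing pain".

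**The concern.** A three-level treatment factor yields more than one test of Hypothesis 1, and the power paragraph does not say which one the 80% belongs to. If the hypothesis is read as a single conclusion about both arms, 80% overstates the chance of reaching it. If a win by either arm is enough, 80% understates that chance, and two unadjusted looks carry more risk of a false claim than one. If exactly one arm wins, whether Hypothesis 1 is supported could be settled after the results are known. The either-or wording in Risk/Benefit Assessment seems to point away from the both-groups wording of Aim 1.

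The comparison with d = 0.38 also invites suspicion. An effect smaller than the detectable one cannot have 80% power in the same calculation.

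**Working it through.** **Inputs.** 100 randomised per arm (Design & Procedures); 10% attrition and d = 0.42 and 0.38 (Data Analysis & Statistical Considerations). Analysed per arm: 100 × 0.90 = 90. Assumed: two-sided alpha 0.05, d in the SD units of the analysis, equal true effects in the two intervention arms.

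**The plan's own figure.** Power ≈ Φ(d/√(2/n) − 1.96), with √(2/90) = 0.1491.

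- d = 0.42: 0.42/0.1491 = 2.817; 2.817 − 1.960 = 0.857; power 80.4% (noncentral t: 80.0%).
- In reverse, 80% at 0.42 needs 89 analysed per arm, and 89/0.90 = 98.9, so 99 randomised against the planned 100.

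The 80% reproduces. Other readings at d = 0.42 do not give it: one-sided 0.05 gives 87.9%, two-sided 0.025 gives 71.8%, both intervention arms pooled (180 v 90) give 90.2%, and no attrition gives 84.4%. The three-arm F test gives 83.4% when one arm, or both equally, differ from control by 0.42. One-sided 0.025 is the same calculation as two-sided 0.05, and it is also what a one-sided 0.05 split over two tests would use.

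**Readings of Hypothesis 1.** The two contrasts share the control arm, so their correlation is (1/90)/(2/90) = 0.5. With p the power of one comparison and B the bivariate normal probability that both win, either = 2p − B and exactly one = 2p − 2B.

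| Reading, no adjustment | d = 0.42 | d = 0.38 |
|---|---|---|
| One arm v control (p) | 80.4% | 72.2% |
| Both arms win (B) | 69.3% | 58.4% |
| At least one arm wins | 91.6% | 86.0% |
| Exactly one arm wins | 22.2% | 27.5% |
| Pooled arms v control | 90.2% | 83.7% |

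Simulation with a shared control and 267 df agrees to within about half a point (both arms 69.0% and 58.1%; exactly one 22.4% and 27.6%).

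**Error rate.** If neither intervention works, the chance of at least one false claim of benefit from two unadjusted tests is 4.5%, against 2.5% for one test. If both arms must win there is no inflation.

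**Baseline covariate.** The plan adjusts for baseline, but its 80% reproduces without any gain from that. If d is in raw SD units, the effect in adjusted units is d/√(1 − ρ²). If it is in change-score SD units, it is d√(2/(1 + ρ)). At ρ = 0.5 the two coincide: 0.38/√0.75 = 0.439, and one comparison then has 83.3% power (noncentral t). The plan gives no ρ. For an assumed ρ of 0.3 to 0.7, power at 0.38 is 76–94% (raw) or 78–88% (change score). It stays at 72% only if d is already in adjusted units or the covariate adds nothing.

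**The case for a change.** The strongest case for a change is that the main hypothesis has no written criterion. If both arms truly have d = 0.42, about one trial in five ends with a single winning arm, and the plan does not say what that means for Hypothesis 1. Writing the rule down before unblinding would cost only wording. The absence is real and the arithmetic stands.

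What it asks for, though, is that the sponsor record whichever rule it prefers: both arms, either arm, or two separate claims with no familywise control. That corrects no wrong rule and commits to no better method. Adjustment for distinct interventions sharing one control is a trade-off. At d = 0.42, closed procedures would lower per-comparison power from 80% to 76–77% if both arms work, or to 71–76% if only one does, before any covariate gain. The unadjusted alternative has a 4.5% chance of a false benefit claim if neither works.

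The argument from d = 0.38 is weaker. The plan does not adopt 0.38 as its design effect and claims no power there. It describes the cited result only as improvement over 3 months, which could be a within-group change; if so, it does not belong in a two-arm power formula. Nor does the sentence in Risk/Benefit Assessment conflict with Aim 1: it describes possible later work and sets no criterion for success.

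**Conclusion.** No change follows. The stated power is correct for what the design delivers: 80% for one intervention against control at d = 0.42, with 90 analysed per arm at two-sided 0.05. That alpha and that comparison are inferred, but of the readings tried only this calculation (or the identical one-sided 0.025) returns the plan's figure. Sizing a multi-arm trial per comparison is ordinary practice, and the plan does not present the 80% as the power of a joint conclusion.

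Outcome, time point, comparator and model are all given. An analyst would take neurofeedback v control and mindfulness v control at 3 months from the treatment-by-month model and report both. The success rule would alter the label put on a one-arm result, not the estimates or their intervals.

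The gap's size depends on inputs the documents do not give. Exactly one arm wins in about 22% of trials at d = 0.42 with equal true effects and no covariate gain, and in as few as 4% at the favourable end of the assumed baseline correlations. The 72% at d = 0.38 also requires that 0.38 be a between-group effect and that the covariate add nothing, neither of which the plan says.

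### Does the sample size fall short because the detectable effect (d = 0.42) is larger than the published effect (d = 0.38) it is matched to?

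*Combined protocol and SAP*

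**What the plan says.** The power statement is in Data Analysis & Statistical Considerations. It begins "After accounting for a 3-month attrition rate of 10" percent and says that "our targeted sample of 300 (100 in each treatment arm) will have 80% power" for a Cohen's d of 0.42. The next sentence compares this with earlier evidence: "This corresponds closely to findings from a published clinical trial of neurofeedback to reduce chronic pain", "which found 3-month improvements in pain intensity (0-10 rating scale) equivalent to Cohen's" d = 0.38. No alpha, sidedness or baseline-to-follow-up correlation is given.

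The same paragraph sets out the analysis: a longitudinal mixed model for change from baseline at 3 and 6 months, with terms for pain stratum, treatment, month and treatment by month, "and baseline score as a covariate". The hypothesis concerns each intervention against control at 3 months.

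The comparator is described under Study Interventions: "The control group will use a Relaxation app, which is designed to promote relaxation". It has the same background sounds, session length and weekly frequency as the neurofeedback app.

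**The concern.** There are three grounds for unease.

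- **The benchmark is below the detectable effect.** A trial with 80% power at 0.42 has less than 80% at 0.38 under the same calculation. The gap of 0.04 looks small, but required sample size scales with 1/d², so it corresponds to (0.42/0.38)² = 1.22, or about 22% more participants.
- **The cited figure may be a different quantity.** It is described as an improvement in pain, with no comparator named. This trial tests a difference from a control app that may itself relieve pain. If 0.38 were a change over time within one arm, the between-arm effect could be smaller.
- **The power figure does not match the planned model.** The 80% comes from an unadjusted two-sample test, whereas the analysis adjusts for baseline.

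If these points held in full, readers would credit the trial with 80% power for an effect of the size seen before, and might read a null result as stronger evidence against the interventions than it is.

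**Working it through.** **Inputs.** From the plan: 100 randomised per arm, 10% attrition at 3 months, 80% power, d = 0.42, cited d = 0.38. Evaluable per arm: 100 × 0.90 = 90. Assumed, because not stated: two-sided alpha of 0.05, with no multiplicity adjustment.

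**Step 1. Reproduce the plan's figure.** For two arms of n each, the noncentrality is d × √(n/2). With n = 90, √45 = 6.708.

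- d = 0.42: 0.42 × 6.708 = 2.817. Normal approximation: Φ(2.817 − 1.960) = 80.4%. Noncentral t: 80.0%.
- Smallest d giving 80% power by noncentral t: 0.420.

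The stated 80% is reproduced. Other settings tried do not give it (noncentral t, d = 0.42): one-sided 0.05 gives 87.7%, two-sided 0.025 gives 71.1%, no attrition gives 84.0%, and both interventions pooled against control gives 90.0%. This supports two-sided 0.05, pairwise and unadjusted, as what was done.

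**Step 2. The same calculation at 0.38.** 0.38 × 6.708 = 2.549. Normal: Φ(2.549 − 1.960) = 72.2%. Noncentral t: 71.7%. An unadjusted test would need 110 evaluable per arm for 80%; 110/0.90 = 122.2, so 123 randomised per arm, or 369 in total against 300.

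**Step 3. Allow for the planned baseline covariate.** If r is the correlation between baseline and 3-month score, adjustment multiplies the residual SD by √(1 − r²). With d standardised by the unadjusted SD, the effective effect is 0.38/√(1 − r²). The document gives no r, so a range is shown (noncentral t, 90 per arm):

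| r (assumed) | √(1 − r²) | effective d | power at 0.38 |
|---|---|---|---|
| 0 | 1.000 | 0.380 | 71.7% |
| 0.3 | 0.954 | 0.398 | 75.7% |
| 0.4 | 0.917 | 0.415 | 79.0% |
| 0.5 | 0.866 | 0.439 | 83.3% |

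Power reaches 80% where 0.420 × √(1 − r²) = 0.38, that is r = √(1 − (0.38/0.420)²) ≈ 0.43.

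**Step 4. The within-arm reading.** Suppose 0.38 is a within-arm change and the control arm achieves 25% or 50% of it. Both shares are assumptions with no basis in the document. Then between-arm d is 0.38 × 0.75 = 0.285 or 0.38 × 0.50 = 0.19, and unadjusted power is about 48% or 24%. With r = 0.5, the 0.285 case rises to 59%. These figures illustrate a possibility. They are not estimates for this trial.

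**The case for a change.** The strongest case for a change is that 0.38 is the only external evidence offered for the effect size. By the plan's own unadjusted method the chance of missing such an effect is about 28%, not 20%, and the sentence invites the reader to overlook that. Baseline adjustment may recover the loss, but the plan claims no such gain and gives no correlation, so a reader cannot tell which side of 80% the trial lies on. Nor does adjustment help if 0.38 is a within-arm change: at d = 0.285 and r = 0.5 power is still only 59%. A short power table would cost nothing in participants.

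Much of this stands. The arithmetic is right, the description of the two effects as close is generous, and the nature of the cited effect is left open. What does not stand is the step to a shortfall. The plan states power at 0.42 only and discloses 0.38 in the next sentence, so setting 71.7% against 80% compares power at two different effects. The 72% also belongs to a simpler test than the one planned. The within-arm argument depends on a source that cannot be consulted here and on invented control responses.

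**Conclusion.** No change to the plan follows. Its one power claim, 80% at d = 0.42 with 90 evaluable per arm, is correct under two-sided 0.05. At the cited 0.38, power is about 72% for an unadjusted comparison and about 76% to 83% for the baseline-adjusted analysis if the correlation lies between 0.3 and 0.5, so the planned analysis may fall slightly short of 80% or slightly above it. Those figures assume the alpha level, the range of r and standardisation of d by the unadjusted SD; the document settles none of these. It also does not settle whether 0.38 is within-arm or between-arm.

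What remains is loose wording in a justification. Stating power at 0.38, alpha, the assumed correlation and the nature of the cited effect would help readers. It would leave the sample size, endpoint, model and conclusions as they are. Any over-reading of a null result is best guarded against by reporting the confidence interval for each intervention-versus-control difference, which does not depend on how this sentence is phrased.
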